Of 18 patients who completed 24-months follow up, 4 are in complete remission, 12 are in partial remission (CR + PR = 80%), 1 had a limited response (>50% drop in P but >3.5g/24h) and 1 patient relapsed from a partial remission. When interpreting these results we should take into account that >50% of these patients had failed previous immunosuppressive therapy. This study also emphasizes that proteinuria is reduced gradually and that it may take several months to reach its nadir. This observation is in agreement with previous reports in patients with IMN treated with prednisone in combination with a cytotoxic agent, but was seen without the short-term toxicity observed with alkylating agents.⁶⁰ Kidney function remained stable or improved in all patients. These results were observed despite the fact that in patients with nephrotic syndrome (NS), serum albumin levels influence tubular creatinine secretion resulting in an endogenous creatinine clearance that overestimates GFR in NS.⁷² In addition, previous investigators have indicated that the onset of IMN is accompanied by a severe depression in hydraulic permeability of the glomerular capillary wall. This is partially offset by enhancement of filtration surface area and by profound depression of glomerular oncotic pressure. This can result in the GFR initially remaining in the normal range or at worst, depressed by <50% in moderate IMN. In severe IMN these investigators found this mechanism was significantly worsened by a marked reduction in functional glomerular number and a GFR depression of >50%. These abnormalities were presumably reversed with RTX treatment and resolution of the NS. However, an additional explanation could have been that a number of patients had their angiotensin II blockade reduced or discontinued with time, altering the renal hemodynamics and thereby contributing to the significant increase in creatinine clearance. The important summary point in this regard is this type of GFR improvement by reduced RASS blockade would not be accompanied by a decrease in proteinuria. RTX therapy represents a substantial advantage versus the risk for nephrotoxicity and other short-term toxicities associated with the use of calcineurin inhibitors (CNI). In addition RTX treatment assures patient adherence (since it is given by IV infusions). This is in contrast to the necessary monitoring required during the treatment with Cyclosporine. This makes

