The goal of this proposal is to conduct a prospective randomized controlled phase III study comparing Rituximab (RTX) to Cyclosporine (CSA) in the treatment of patients with IMN. Once a patient with IMN and proteinuria $\geq 5\text{g}/24\text{h}$ is identified, meets other entry criteria and consents to the study, he/she will receive a minimum of 3 months of conservative therapy aimed at maximizing Angiotensin II blockade (run-in phase). If at the end of this period the patient still meets entry criteria he/she will be randomized into a 12-month treatment period, and a subsequent follow-up of 12 months. Efficacy of treatment will be assessed by remission status (based on changes in proteinuria) at 24 months from randomization. Patient safety will be assessed via collection of adverse event data and evaluation of pre- and post-treatment laboratory data. At the 6-month post-randomization visit, patients who have been randomized to either CSA or RTX but who do not have a reduction in proteinuria $\geq 25\%$ (confirmed on repeat measurements within 2 weeks) will be considered treatment failures and exit the study. Data from that point onward will be censored. Patients in the RTX group who have a reduction in proteinuria of equal to or $>25\%$ at 6 months will be given another identical course of RTX (1g x 2). This treatment regimen was chosen given our initial data that suggested a percentage of our cohort appeared to respond to an additional course of therapy. Data from our 2 pilot studies showed that RTX is out of the circulation by month 2 in the majority of patients and B cells have recovered by month 3 in patients treated with RTX 1g x 2 (the regimen chosen for the study). Thus, at 6 months, patients in the RTX arm are completely, at least as best as we can measure, free of immunosuppression, and hence the second course should not be associated with additive toxicity. The same definition of response will apply to the CSA arm at 6 months. An equal to or $>25\%$ reduction in proteinuria will dictate continuation of the CSA for an additional 6 months (total of 12 months of full dose CSA). This assessment at six months allows a balance between risk-benefit in both arms. The protocol provides similar exposure to immunosuppression in both arms and allows an early exit for patients related to safety issues by providing a lack of efficacy (futility) end point at 6 months.

Primary endpoint

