Rituximab: Patients randomized to the RTX arm will receive 1000 mg IV on Days 1 and 15. Patients who achieve complete remission at 6 months will not be retreated. A second course of RTX 1000 mg IV will be administered at study month 6 for individuals who have not achieved a complete remission, but have achieved at least a $\geq 25\%$ reduction compared to their central laboratory (Mayo Clinic Rochester) baseline (Time 0) proteinuria (but not a CR). Dosing at study month 6 will be independent of CD19/20+ B cell count. The rationale for retreating patients who have had an equal to or $> 25\%$ reduction in proteinuria at 6 months is based on our experience in our pilot studies (first study using 1000 mg on Days 1 and 15 and second study using 4 weekly doses of $375\text{mg}/\text{m}^2$) where an increase in the proteinuria remission rate was achieved after a second course of treatment. In our 2 studies repeated courses of RTX were not associated with additive adverse effects in comparison to their first course. If after six months the reduction in proteinuria is less than 25% compared to baseline the RTX treatment will not be repeated, the patient will exit from the study and will be considered a failure of therapy.

Dosage and Administration of Rituximab: The first infusion of both courses (Day 1 and Day 181) of RTX will be administered IV at an initial rate of 50 mg/hr. All patients

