CSA was 175 ng/ml the goal would be to reduce it to 130 ng/ml by reducing the dose by approximately 25% - dose reduction is approximate because CSA is only available in specific dose strengths (25mg, 100mg) and therefore some rounding may be required). If with this dose reduction the creatinine does not return to within 30% of baseline levels within 3 weeks, then a second dose reduction of approximately 25% with a similar reduction in CSA trough level (e.g. if CSA trough level was 100 ng/ml, reduce to 75 ng/ml) will be used. If the creatinine does not fall to within 30% of baseline values with this second dose reduction, the drug will be discontinued. If after six months the reduction in proteinuria is less than 25% compared to baseline the drug will be discontinued, the patient will exit from the study and be considered a failure of therapy. At the end of 12 months, Cyclosporine will be tapered by 1/3 of the maintenance dose monthly and hence discontinued after 2 months. Serum potassium and serum creatinine levels will be checked at the initiation of Cyclosporine in conjunction with blood draw for CSA level. If Cyclosporine dose is changed during treatment, potassium, creatinine and CSA levels will be rechecked every two weeks +/- 3 days post increase/decrease in CSA dosage until levels are stable and at target.

[figure not shown]

Figure 4. Schematic representation of the study design.

Blinding

This will be an open-label study with neither patients nor physicians blinded. Blinding, for this study, was considered difficult and unnecessary and would significantly add to the cost of the study. The need to provide RTX intravenously would require that the CSA arm patients would have to receive an IV infusion of saline which seems unjustifiable from the scientific and budgetary points of view. Furthermore, with the exception of

quality of life measures, all endpoints are based on objective (laboratory) criteria. Having the physicians in the study blinded to CSA level also introduces a potential risk factor that's unnecessary in our estimation. Documentation of cyclosporine levels will ensure that patients are taking the drug at the appropriate time and achieving the prescribed levels indicated in the protocol.

Pharmaceutical logistics

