For those patients in the Cyclosporine arm, **Cyclosporine trough level measurements will be done every 2 weeks +/- 3 days after initiation of Cyclosporine until levels are stable and at target. Potassium and creatinine will also be checked in conjunction with CSA level. If Cyclosporine dose is changed during treatment, potassium, creatinine and CSA level will be rechecked every 2 weeks +/- 3 days until levels are stable and at target.** Cyclosporine levels will also be assessed whenever serum creatinine rises by $>30\%$ without a recognizable reason such as volume depletion, additional drugs, sepsis, etc. Patients who cannot tolerate the medications and/or who are treatment failures at 6 months will exit the study at 6 months (i.e., the 6 month visit and accompanying data collection should still occur). Patients who go in to complete remission will discontinue study drug but will continue with full visit follow-ups until month 24 as scheduled. However, the therapeutic/management plan for these patients will be solely at the discretion of the managing nephrologist although while in CR no further immunosuppressive therapy is recommended. Likewise, patients who relapse from either a partial or complete remission or who are not in partial or complete remission by the end of the treatment period (i.e., 12 months) will continue with the visit schedule, but the therapeutic/management plan will be solely at the discretion of the managing nephrologist. Finally, for patients who temporarily stop taking Cyclosporine, there are three possible scenarios:

1. Patients who discontinue Cyclosporine for < 2 weeks may simply be restarted on the study drug and continue to fully participate in the trial. The treatment is to be restarted at its former dose and the patient returned to the regularly scheduled follow-ups including the periodic sampling for assessing potassium, creatinine and CSA trough levels.
2. Patients who discontinue Cyclosporine for ≥ 2 weeks, but < 4 weeks may also be restarted on the study drug at its former dose and fully participate in the trial, but the temporary discontinuance will be logged as a protocol deviation and the missed treatment days will be made up at the end of month 12. This is to ensure that all patients receive approximately 12 months of treatment with study drug.

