Adverse events (both patient and event counts) will be tabulated by body system, severity and, for each severity, by investigator-assessed relationship to study drug. Group comparisons for adverse events with 4 or more occurrences will be done using chi-square or Fisher's exact test. The last RTX injection is at 6 months and the tapering of Cyclosporine will be completed by the end of month 14. Hence, the adverse events analyses will focus on events through month 18, allowing these additional months for potential lingering Cyclosporine or RTX complications.

The analysis of the primary endpoint (urine protein failure at month 24) will be intent-to-treat (ITT), and will include all randomized subjects in the analysis. For those without a 24 month visit, the 18 month visit results will be used if available, otherwise they will be assumed to have failed at 24 months. Per protocol (PP) analyses will also be done including only those subjects who receive a full course of study medication and who have a 24 month visit.

Interim analyses: No interim analyses for efficacy will be performed during the trial, however safety data will be compiled and reviewed approximately every six months or at the request of the Data and Safety Monitoring Board.

Investigator and Coordinator Training: In order to make efficient use of funding, annual investigator and coordinator meetings will be coordinated with national nephrology meetings where possible. It is expected that the majority of the training will occur through web-based technology and will be coordinated through the data management and coordinating Center.

The **Data Management and Coordinating Center (DMCC)** is located at the Applied Health Research Center (AHRC) at St. Michael's Hospital/University of Toronto. The DMCC will be responsible for facilitating all aspects of the study planning, training, implementation, data collection and analysis.

The clinical information collected for this study will be stored at the DMCC at the Applied Health Research Centre of St. Michael's Hospital in Toronto, ON, Canada and also sent to a federal data repository held by the Office of Rare Diseases Research (ORDR) and located at the University of South Florida (USF) in Tampa, FL.

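### Adverse events are compared by chi-square or Fisher's test over 18 months although month-6 exits are seen for only 6, so unequal exits would make the arm with more of them look safer than it is

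*Combined protocol and SAP*

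**What the plan says.** The Statistical and Analytical Plan sets out the safety analysis in a few sentences. "Adverse events (both patient and event counts) will be tabulated by body system, severity" and by relationship to study drug. "Group comparisons for adverse events with 4 or more occurrences will be done using chi-square" or Fisher's exact test. Because cyclosporine (CSA) taper ends by month 14, "the adverse events analyses will focus on events through month 18".

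Follow-up is not planned to be equal over that window. Overall Research Design and Methods says that patients in either arm without a confirmed reduction of at least 25% at month 6 "will be considered treatment failures and exit the study. Data from that point onward will be censored". The treatment descriptions repeat the exit for rituximab (RTX), "the patient will exit from the study and will be considered a failure of therapy", and for CSA, "the patient will exit from the study and be considered a failure of therapy". Patient monitoring and evaluation adds a second group: "Patients who cannot tolerate the medications and/or who are treatment failures at 6 months will exit the study at 6 months".

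The plan names no person-time rate, no time-to-first-event analysis and no denominator rule for patients who have exited.

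**The concern.** A chi-square or Fisher's test on patient counts treats each patient as observed for the whole window. A patient who exits at month 6 without an event has only a third of the window (6 of 18 months) observed. On the natural reading that patient stays in the denominator as event-free. If one arm loses more patients this way, its crude proportion is lowered more.

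Specific Aim 4 is that RTX has the better side-effect profile, and adverse events are a listed secondary endpoint. Unequal exits could produce part of a safety difference in either direction, or hide part of a real one. Elsewhere the plan does allow for unequal follow-up: mixed models are chosen for slopes because the number of readings varies, and the primary endpoint has a rule for missing month-24 visits. Adverse events have no such rule.

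**Working it through.** **The plan's own figure.** Sample size estimation states 80% power for a difference of around 0.25 in proportions with 63 per arm. Take 37.5% against 62.5%, two-sided 0.05, so the average proportion is 0.5:

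- Null standard error: √(2 × 0.5 × 0.5 / 63) = 0.0891.
- Alternative standard error: √((0.375 × 0.625 + 0.625 × 0.375) / 63) = 0.0863.
- Power: Φ((0.25 − 1.96 × 0.0891) / 0.0863) = Φ(0.874) = 80.9%.

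The figure reproduces, on the footing that everyone is seen for the full window.

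**Inputs for the bias.**

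- Window 18 months, exit at month 6: from the documents.
- Exit share e by arm: not given. Assumed 35% in one arm and 20% in the other, with either arm higher.
- First-event hazard: not given. Assumed h₁ in months 0–6 and h₂ in months 6–18, the same in both arms. A hazard of 0.02 per month gives 30.2% at 18 months, close to the figure of up to 20–30% for frequent CSA effects under Toxicity of cyclosporine. A hazard of 0.05 gives 59.3%, nearer to any adverse event than to one event type.

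**Formulas.** P6 = 1 − exp(−6h₁). P18 = 1 − exp(−6h₁ − 12h₂). Crude proportion = e × P6 + (1 − e) × P18. With equal true risk, the false gap = (difference in e) × (P18 − P6).

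| Assumed hazard per month | P6 | P18 | Crude, 35% exits | Crude, 20% exits | False gap |
|---|---|---|---|---|---|
| 0.02 throughout | 11.3% | 30.2% | 23.6% | 26.4% | 2.8 points |
| 0.05 throughout | 25.9% | 59.3% | 47.6% | 52.7% | 5.0 points |
| 0.05, then 0.0125 | 25.9% | 36.2% | 32.6% | 34.2% | 1.5 points |
| No first events after month 6 | P6 = P18 | | | | 0 |

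Gaps are from unrounded values. Equal exits give zero in every row. A wider split of 40% and 15% gives 4.7 points at 0.02, 8.4 at 0.05 (46.0% against 54.3%) and 2.6 in the falling-hazard case.

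**Effect on the test.** By exact enumeration at 63 per arm, 47.6% against 52.7% gives a significant chi-square favouring the arm with more exits 9.1% of the time. With exits of 20% in both arms the figure is 2.9%.

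**Masking.** Suppose the arm with more exits is truly worse, 62.5% against 37.5%, with assumed exits of 30% and 10% and constant hazards. Then P6 = 1 − 0.375^(1/3) = 27.9% and 1 − 0.625^(1/3) = 14.5%. The crude proportions are 0.7 × 62.5 + 0.3 × 27.9 = 52.1% and 0.9 × 37.5 + 0.1 × 14.5 = 35.2%. The 25-point difference shrinks to 16.9 points, and power falls from 80.9% to 48%.

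**Whether patient-month rates would repair it.** Planned observation is 18 − 12e months: 13.8 at 35% exits and 15.6 at 20%. If all events are early and identical in the two arms, events per patient-month give a spurious ratio of 15.6 / 13.8 = 1.13 against the arm with more exits. At 40% and 15% it is 16.2 / 13.2 = 1.23. A constant-rate analysis can therefore err the other way.

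**The case against.** The strongest reply is that unequal exits are conjecture. A reader might infer that RTX will lose more patients at month 6, and so gain a false safety advantage, because the pilot report says that "proteinuria is reduced gradually and that it may take several months to reach its nadir". The documents do not support that. The sentence concerns time to the lowest proteinuria under the four-dose pilot regimen, whereas exit turns on failing a 25% reduction. Sample size estimation describes the 12-month RTX response as close to that of calcineurin inhibitors. The only proxies overlap: 5 of 14 RTX pilot patients without remission at 12 months (36%), against 25–40% left by a 60–75% CSA remission rate. Both use a different definition from the exit rule. At a hazard of 0.05 they give anything from 0.11 × 33.4 = 3.7 points in favour of RTX to 0.04 × 33.4 = 1.3 points in favour of CSA.

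Timing also limits the size. The commonest RTX effects in the pilots were infusion related, and exiting patients stop study treatment, so a constant hazard to month 18 may be too high. Intolerant patients will often have had a counted event already, which shrinks the bias further.

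That exits count as event-free is the natural reading of these tests, not stated text. Event counts are tabulated too, but without exposure they carry the same problem. Three other provisions soften the point without closing it. Adverse event reporting runs from Time 0 to study termination, but does not say that collection continues after a patient's own exit. Subject Discontinuation follows patients until existing events resolve, which does not cover new ones. Stopping points for medications encourages follow-up for those who stop by choice or are withdrawn for adverse events, and does not name month-6 failures.

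**Conclusion.** The point holds as a conditional one. The planned tests ignore a planned exit at one third of the window. They are distorted whenever exit shares differ by arm and some first events fall after month 6, and the arm with more exits then looks safer than it is. The direction cannot be read from the documents, and a claim that the design favours RTX would go beyond them.

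Under the assumed 35% and 20% exits the false gap is about 1.5 to 5 points, and it is zero with equal exits or no late first events. That is small beside the 25 points for which these comparisons are sized, but enough to raise the chance of a false finding or dilute a true one. Exit shares, hazards and their timing are all assumptions. The correction is worth making because Aim 4 rests on this comparison and the change is cheap.

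**What to change.** Amend the Statistical and Analytical Plan so that the between-arm comparison of adverse events consists of:

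1. the proportion of randomized patients with an event in months 0–6, before the planned failure exits; and
2. time to first event through month 18, shown as cumulative incidence, with censoring at exit.

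Show person-time by arm, split at month 6. Keep the crude 18-month proportions and any patient-month rates as descriptive tables only, since a constant-rate analysis over-penalises the arm with more exits when events are early.

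The plan should also acknowledge that censoring at exit may be informative, because exit follows from non-response or intolerance; the months 0–6 comparison does not depend on the handling of the failure exits. It should state whether adverse events are collected after a month-6 exit. Patient monitoring and evaluation (intolerant patients exit at month 6) and Stopping points for medications (patients withdrawn for adverse events are encouraged to stay in follow-up) must be reconciled.

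The cost is SAP wording and a few extra tables, with no added patients or visits. It assumes that event and exit dates are recorded, which the documents do not state outright.

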CR or PR (defined as per table 1) at 24 months after randomization will be the primary endpoint. This will be assessed in an intention to treat (ITT) analysis.

Secondary endpoints

1. Relapse state at month 24 after randomization (Urine Protein (UP) $> 3.5\text{ g}/24\text{h}$ after earlier CR or PR)
2. Anti-PLA2R levels
3. Quality of life as measured by modified KDQOL
4. Adverse events

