5. ESRD
6. CR or PR, and CR alone at 6, 12, 18, and 24 months after randomization
7. Time to CR or PR
8. Effect of treatment on renal function, as assessed by slope of creatinine clearance from baseline to 24 months.

Table 1. Definition of remission status

Remission status	Proteinuria (UP g/24 hours) after treatment
Complete remission (CR)	UP \leq 0.3 g/24h and serum albumin \geq 3.5g/dl
Partial remission (PR)	Reduction in baseline UP of \geq 50% plus final UP \leq 3.5 g/24h but $>$ 0.3 g/24h
Non-response (NR)	Reduction in baseline UP of $<$ 25% (includes increase in UP)
Relapse	Development of nephrotic range proteinuria following CR or PR, i.e. $>$ 3.5g/24h

Patient recruitment

The study population will be comprised of individuals with biopsy-proven idiopathic MN. Total study size will be 126 patients, enrolled among up to 25 participating sites. Potential candidates for the study will be identified by the investigators using existing databases and clinical trial networks. The P.I. or the study coordinator will contact these potential candidates and if the preliminary interview indicates their willingness to participate, a consent form will be reviewed with the patient. If a potential candidate remains interested, the consent form will be signed, and the patient enrolled in the study. The institutional review board at each participating site will approve the recruitment process and consent forms. The Mayo Nephrology Collaborative Group (MNCG) will post information on its web site describing the study and identifying local contacts at the collaborating centers. Each site involved may have their own methods of informing and recruiting potentially eligible patients but in all cases will have IRB approval before embarking on this process. Each site will be expected to randomize approximately 6-10 patients over the recruitment period. If, based on site estimates of the IMN population that would be eligible for this study, we enroll approximately 30% of the annual population in a single year our recruitment will be complete. We have assembled a consortium for this trial with a population that well exceeds the enrollment needs based upon the multi-year enrollment plan for this trial.

Recruitment strategy

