Sample size estimation: The primary study goal is to compare the long-term efficacy of RTX (given at baseline and repeated at 6 months) with CSA (12 months treatment + 2 months taper) using proteinuria response 24 months after randomization. Proteinuria positive response will be defined as attaining and maintaining CR or PR at 24 months after randomization. We propose to establish that the RTX treatment is non-inferior to the CSA. RTX will be considered non-inferior to CSA if the response rate of the RTX arm is at most 15% worse than that of CSA arm. In addition we will compare the quality of life (QOL) and adverse event (AE) profile over the course of the treatment period. The preliminary data has indicated that CSA is effective in inducing a CR/PR of proteinuria in between 60 and 75% of MN cases.^{48, 51} However, nephrotic syndrome (NS) relapses may be as high as 50% once CSA is discontinued.⁸⁵ Thus, we estimate a CR/PR rate in patients treated with CSA of 30-50% at 24 months after randomization.⁸⁵ Similar remission and relapse rates with the use of Tacrolimus (another calcineurin inhibitor) have been reported by Praga et al.⁵⁶ In this latter study, almost half of the MN patients had a relapse of the nephrotic syndrome after tacrolimus was discontinued.⁵⁶ On the other hand, based on the long term follow up on the 35 patients treated with RTX from our 2 studies, we estimate the relapse rate to be <10% at 24 months.^{71, 75} We observed a CR/PR rate at 12 months, very similar to the rate for calcineurin inhibitors i.e. 60%, and in our second study completed recently, we observed an 80% CR/PR rate at 24 months, implying that RTX had a ~20% failure rate with 95% (CI 6% to 44%). To be conservative for the sample size estimation, we considered a maintained CR/PR rate at the low end of our previous experience, 55% CR/PR for RTX at 24 months and at the high end of our experience with CSA (CNI therapy) CR/PR for CSA of 45%. We propose a non-inferiority trial with non-inferiority margin $\delta = 15\%$, with the null hypothesis of $\pi_{RTX} - \pi_{cyclosporine} < \delta$, where π_{RTX} and $\pi_{cyclosporine}$ are the proportions of patients with CR/PR at 24 months in treatment arms of RTX and CSA, respectively. Under these assumptions, and a one sided alpha of 0.025, enrollment of 63 evaluable patients per study arm is required to achieve 80% power to show that the RTX is not inferior. For the intent to treat (ITT) analysis we will consider all patients lost to follow up to be non-responders so no correction to the sample size is needed for dropouts. With 63 patients per arm we will have 80% power to detect moderate differences of .6 standard deviations for continuous measures or around .25 for proportions for the comparisons of the QOL and AEs.

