
Statistical and Analytical Plan: All demographics and entry laboratory data will be summarized by treatment group. Frequency distributions will be used to describe categorical values and basic summary statistics (mean, standard deviation, median, and inter-quartile range) will be used to describe continuous values. To provide more reliable estimates and minimize the “regression to the mean effect” duplicate urine measurements obtained at baseline (Time 0), 6, 12, 18 and 24 months will be averaged. The chi-square test and logistic regression will also be used to compare the percent of patients with remission at 6, 12, 18, and 24 months adjusting for treatment center and the baseline

proteinuria (UP<8g/24h vs >=8g/24h). Odds ratios and associated 95% confidence intervals will be estimated. The formal test for the primary endpoint will be based on the significance of the treatment group factor in the logistic regression model for UP failure at month 24. The Wilcoxon rank-sum test and ordinal logistic regression will be used to compare the ordered remission status outcome (1=CR, 2=PR, 3=NR) between treatment groups. Longitudinal methods for categorical outcomes (e.g. generalized estimating equation or GEE models) will be used to compare remission status profiles between treatment arms. Unless otherwise noted, all tests will be two-sided with alpha level 0.05.

For repeated measures such as urine protein, individual rates of change will be estimated using within-patient linear regression analyses (including data from all visits). Because of the non-linearity of the changes in proteinuria log transformation estimates will be used. Renal function readings will be censored at initiation of dialysis or renal transplant. Additionally, mixed effects models, assuming a random center effect, and a random slope of creatinine clearance and/or reciprocal of creatinine and intercept for each patient will be fit using data from all visits. These models allow comparison of the average slope between groups, while taking into account that each patient's slope may be based on a variable number of readings. Treatment group comparisons regarding quality-of-life scales will be done using repeated measures analyses and mixed effects models.

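### The month-18 carry-forward, and a remission definition with no kidney-failure condition, can score a patient who has died or reached dialysis or transplant as a success at month 24

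*Combined protocol and SAP*

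**What the plan says.** - **Endpoint.** Under Primary endpoint: "CR or PR (defined as per table 1) at 24 months after randomization will be the primary endpoint". Table 1 sets its criteria in a column headed "Proteinuria (UP g/24 hours) after treatment". CR needs urine protein of at most 0.3 g/24h and serum albumin of at least 3.5 g/dl. PR needs a fall of at least 50% to a value of at most 3.5 but above 0.3 g/24h. Neither requires the patient to be free of dialysis or transplant. ESRD is a separate secondary endpoint.
- **Missing month 24, Statistical and Analytical Plan (ITT).** "For those without a 24 month visit, the 18 month visit results will be used if available". Only a patient with neither result counts as a failure.
- **Missing outcome, Sample size estimation (ITT).** "we will consider all patients lost to follow up to be non-responders". The same section requires the response to be both reached and held at 24 months. It does not say whether death, dialysis or transplant counts as loss to follow-up.
- **Dialysis and transplant.** The one analysis rule that names them is "Renal function readings will be censored at initiation of dialysis or renal transplant". It concerns the renal function analyses, not remission status.
- **Discontinued patients.** Subject Discontinuation keeps data collected before discontinuation in the primary analysis unless consent is withdrawn.

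**The concern.** The protocol justifies remission as the endpoint because it is a surrogate for renal survival (Background; Cyclosporine section). A rule that can record death or kidney failure as remission works against that reason. There are two separate routes.

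1. **Carry-forward.** The patient is in CR or PR at month 18, dies or reaches kidney failure afterwards, and has no month-24 visit. The month-18 remission becomes the month-24 result.
2. **Direct scoring.** The patient is on dialysis or has a transplant, from any time in the study, and attends month 24. Under Laboratory testing, 24-hour protein is calculated from an aliquot and the collection volume, so at a given concentration a smaller volume gives a smaller total. If the value meets Table 1, the patient is CR or PR. The check on collections compares the two specimens' creatinine with each other, so two consistently low collections would pass it.

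At stake are a few patients in a binary comparison of 63 per arm with a 15-point margin, where one patient can change the conclusion near the boundary.

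**Working it through.** **Step 1. Read the rules side by side.** Take a patient in PR at month 18.

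| Course after month 18 | Statistical and Analytical Plan | Sample size section |
|---|---|---|
| Dies in month 20 | Success (month 18 carried forward) | Failure if death is loss to follow-up; not stated |
| Starts dialysis, no month-24 visit | Success | Failure if this is loss to follow-up; not stated |
| Dialysis or transplant, attends month 24, protein within Table 1 limits | Success | Rule does not apply; the patient is not lost |
| Not in remission at month 18, no month-24 visit | Failure | Failure |

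The first two rows are a conflict between sections. The third is a gap in Table 1, and it also covers dialysis or transplant before month 18.

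**Step 2. Reproduce the planned size.** Inputs from Sample size estimation: rituximab 55%, cyclosporine 45%, margin 15 points, one-sided alpha 0.025, power 80%.

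n = (1.960 + 0.842)² × (0.55×0.45 + 0.45×0.55) / (0.10 + 0.15)² = 62.16, so 63 per arm. The stated figure reproduces. Power at 63 is 80.5%.

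**Step 3. Effect of one patient.** 1/63 = 1.59 points, and 1.59/15 = 10.6% of the margin. With 28/63 responders on cyclosporine (unpooled 95% limits on the difference):
- rituximab 30/63: lower limit −14.2 points, non-inferior;
- rituximab 29/63: lower limit −15.8 points, not shown.

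**Step 4. Direction.** Let k be the event patients counted as responders in an arm. The documents give no value, so k = 1 to 3 is an assumption. Power = Φ[(pR − pC + 0.15)/SE − 1.96], with SE² = pR(1−pR)/63 + pC(1−pC)/63. The first three columns start from the planned 55% and 45% and rescore the k patients as failures. The last takes a true difference of −15 points (30% against 45%) and wrongly adds k responders on rituximab.

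| k | Power, k on rituximab rescored | Power, k on cyclosporine rescored | Power, k in each arm rescored | One-sided type I error, k on rituximab misscored |
|---|---|---|---|---|
| 0 | 80.5% | 80.5% | 80.5% | 2.5% |
| 1 | 75.1% | 85.2% | 80.6% | 3.8% |
| 2 | 69.0% | 89.1% | 80.7% | 5.6% |
| 3 | 62.5% | 92.2% | 80.9% | 7.9% |

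Misscoring on rituximab makes a false claim of non-inferiority easier. Misscoring on cyclosporine raises the comparator rate and makes the claim harder. Equal numbers in both arms nearly cancel.

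**Step 5. How many patients.** The Cyclosporine section cites 10-year renal survival of 100% after CR and 90% after PR. At a constant hazard (assumption), six-month risk in PR is 1 − 0.90^(0.5/10) = 0.5%. Use the planned month-24 responders as a stand-in for month-18 remitters, all taken as PR:
- rituximab: 0.55 × 63 ≈ 35, and 35 × 0.0053 = 0.18 patients;
- cyclosporine: 0.45 × 63 ≈ 28, and 28 × 0.0053 = 0.15 patients.

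If all 63 patients in an arm were in PR at month 18, the figure would be 63 × 0.0053 = 0.33. This covers kidney failure by the carry-forward route only. The documents give nothing from which to bound deaths or the direct route.

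**The case against.** **The sample size section already fails these patients.** This is the best argument on the other side. Read alone, with its requirement that remission be held at 24 months, it arguably makes a month-20 death a non-responder. So a reader might infer that the plan clearly counts deaths as successes, and the documents do not support that: they contain two rules that disagree. But the carry-forward rule is the more specific one, and nothing says which prevails. The sample size rule also cannot reach a dialysis or transplant patient who attends.

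**Harm is reported elsewhere.** This stands. ESRD is a secondary endpoint, adverse events including death are reported to study termination, and the DSMB reviews safety. A proteinuria endpoint with ESRD kept separate is an argued choice, and this point does not ask for a different kind of endpoint. Separate reporting does not correct the primary result, however, and the adverse event analyses focus on events through month 18. The per-protocol set does not help either: it needs a month-24 visit, so it drops deaths instead of failing them, and it keeps attending dialysis or transplant patients who had a full course.

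**Events will be rare.** This also stands. Entry needs eGFR or creatinine clearance of at least 40, patients with less than a 25% proteinuria reduction leave at month 6, and carry-forward needs remission at month 18. The direct route further depends on urine protein actually being low after kidney failure, which the documents do not discuss.

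**Conclusion.** The point holds as a defect in the scoring rules, with a small expected effect. Followed as written, the Statistical and Analytical Plan makes a month-18 remitter who then dies or reaches kidney failure without a month-24 visit a success, in conflict with the sample size section. Table 1 independently allows a dialysis or transplant patient with low 24-hour protein to be CR or PR. Each such patient is worth 1.6 points. Kidney failure by the carry-forward route is likely below one patient per arm, assuming a constant hazard and the renal survival cited after PR. Deaths and the direct route are unquantified.

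Two stronger readings should be resisted.

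- A reader might infer that the rule hides harm from a nephrotoxic comparator and so favours rituximab. The arithmetic runs the other way: misscored cyclosporine events make non-inferiority harder to show. A false claim needs an excess of such events on rituximab, and the documents give no reason to expect one.
- A reader might take the 25% ESRD at 8 years cited in Background and derive 1 − 0.75^(2/8) = 6.9%, or 4.4 of 63 patients, by two years. That cohort was untreated. It does not describe patients in remission at month 18, nor patients kept on study for a month-6 response.

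No stated figure is wrong, and 63 per arm stands.

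**What to change.** Before analysis, add to the primary endpoint definition and the ITT paragraph:

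- Death from any cause, dialysis or kidney transplant before the month-24 assessment is a failure, whatever the measured proteinuria.
- The month-18 result is never carried forward after any of these events.
- One missing-data rule replaces the two now in Sample size estimation and the Statistical and Analytical Plan, and says which absences it covers.

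State whether a short course of dialysis with recovery counts as an event. Score CR/PR at months 6, 12 and 18 the same way for consistency, and report the number of these events by arm beside the primary result.

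The cost is a few sentences. ESRD and deaths are already collected, so no new data are needed. A response rate may fall by a patient or so, and the required sample size does not change. Settling the rule before outcomes by arm are seen avoids a dispute over individual patients later.
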